6.4.4.4.2 Suspected Infection with CRS-207 or Listeria

In the case of a suspected persistent CRS-207 or Listeria infection that has not been confirmed by culture, collection of blood, urine and stool samples in duplicate is recommended. One set of samples should be cultured locally for Listeria per institutional guidelines. Culture of cerebrospinal fluid should be obtained for subjects with suspected central nervous system infection. In such instances, analysis of cerebrospinal fluid should also include cell count, protein, glucose, and Gram stain. If samples are positive for Listeria, the Sponsor must be notified immediately, and the duplicate samples and Listeria isolate must be sent to Sponsor or designee for testing to confirm CRS-207. Instructions on collection, storage and shipping of samples for CRS-207 testing are provided in the Central Laboratory Manual.

If infection with CRS-207 is confirmed or suspected, IV antibiotics ([Section 6.3.6](#)) should be initiated as soon as possible and follow-up cultures obtained periodically to confirm absence/clearance of any CRS-207 infection. The Medical Monitor should be consulted regarding continuation of study drug treatment and treatment of suspected or confirmed infection.

6.4.5 Appropriateness of Measures

Tumor imaging is the gold standard for assessing monitoring disease progression and tumor response in patients with cancer. The primary efficacy variable, ORR, is generally an accepted surrogate of efficacy appropriate for use in single-arm studies with smaller sample sizes ([Food and Drug Administration, 2007](#)). Tumor response will be evaluated using both RECIST v1.1 and irRECIST. The inclusion of irRECIST accounts for the unique tumor response characteristics

reported for immune checkpoint inhibitors such as pembrolizumab ([Nishino, 2013](#)). Immunotherapeutic agents such as pembrolizumab may produce antitumor effects by potentiating endogenous cancer-specific immune responses. The response patterns seen with such an approach may extend beyond the typical time course of responses seen with cytotoxic agents, and can manifest a clinical response after an initial increase in tumor burden or even the appearance of new lesions. Therefore, the standard RECIST v1.1 may not provide an accurate response assessment of immunotherapeutic agents such as pembrolizumab.

Additional secondary efficacy variables will also be derived from tumor imaging and response assessments. OS is the universally accepted direct measure of benefit and is an objective measure, although may be limited by difficulties with patient follow-up in smaller studies and confounded by non-cancer deaths in long-term studies.

Paired tumor biopsies and archival tissue will be analyzed for PD-L1 expression as well as other immune checkpoint molecules and infiltration of immune cells (e.g. T cell, myeloid and DC subpopulations) by IHC and gene expression profiling. PD-L1 expression may predict response to anti-PD-1 ([Brahmer, 2010](#); [Topalian, 2012](#)). PD-L1 is also upregulated in response to IFN- γ released by infiltrating T cells and could potentially be a predictor of response to any active immunotherapy. Characterization of immune checkpoint expression as well as immune infiltrates may be predictive of response to therapy and may also give insight into next generation combinatorial approaches.

The safety parameters to be evaluated in this study include standard assessments such as recording of medical history, AEs and SAEs, physical examination, vital signs, ECGs, serum chemistry and hematology, urinalysis, concomitant medications, and other routine clinical and laboratory procedures.

6.5 Statistical Analysis

The completeness of the data affects the integrity and accuracy of the final study analysis. Therefore, efforts will be made to ensure complete, accurate and timely data collection, and to avoid missing data. The procedures for handling missing, unused, or spurious data, along with the detailed method for analysis of each variable, transformations, and exploratory analyses will be presented in the Statistical Analysis Plan (SAP); the information below is intended as a guide to planned analyses.

6.5.1 Sample Size Determination

This study is descriptive in nature, as such the sample size for this study is determined by practical rather than statistical considerations. Approximately 79 subjects will be enrolled to achieve at least 79 treated subjects with evaluable post-baseline tumor data. With 79 subjects, the precision for point estimate for ORR is as follows: the 95% confidence interval (CI) width for ORR based on Wilson score intervals are at most the observed proportion +/- 0.108. If the

observed ORR = 30.4% (24 of 79 subjects with PR or CR), the lower bound of the 95% CI would be 19.5%.

Of the 79 subjects enrolled, an estimated 50 subjects will be enrolled with gastric or GEJ cancer, and an estimated 29 subjects will be enrolled with esophageal cancer. Assuming at least 50 evaluable gastric/GEJ subjects are evaluable for ORR, the precision for point estimate for ORR is as follows: the 95% CI width for ORR based on Wilson score intervals are at most the observed proportion +/- 0.134. Assuming at least 29 evaluable esophageal cancer subjects are evaluable for ORR, the precision for point estimate for ORR is as follows: the 95% CI width for ORR based on Wilson score intervals are at most the observed proportion +/- 0.173.

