6.2 Study Population

The population for this study will consist of approximately 79 adults with recurrent or metastatic gastric, GEJ, or esophageal adenocarcinomas who have received one or two prior systemic chemotherapy treatment regimens for advanced disease. Due to overlap in the diagnosis of esophageal, GEJ, and gastric cancers, the study population will consist of adenocarcinomas from all 3 anatomic sites; however, enrollment will be targeted to a minimum of 26 subjects with esophageal cancer (the less prevalent phenotype) to balance the study population. Prior treatment must have included a platinum and a fluoropyrimidine since this is approved therapy and recognized as standard of care in clinical practice. Similarly, eligible subjects must have tumor which are HER-2/neu negative or, if HER-2/neu positive, disease must have previously progressed on treatment with trastuzumab.

Individuals with immunosuppressive disorders or who require immunosuppressive medications will be excluded. An Eastern Cooperative Oncology Group (ECOG) performance status of 0 or 1 and serum albumin levels serve as prognostic indicators of participants more likely to benefit from treatment.

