6.5.2 General Considerations

The descriptive summary for the categorical variables will include counts and percentages. The descriptive summary for the continuous variables will include means, medians, standard deviations, Q1, Q3, and minimum and maximum values. The descriptive summaries of time to event data will include median, 25th and 75th percentiles, and standard error. All data will be listed for all subjects.

This study is descriptive in nature; no formal hypothesis testing will be performed. All CIs will be 95%, unless stated otherwise.

All statistical analyses will be performed using SAS.

The effects of noncompliance, dropouts, and covariates will be assessed to determine the impact on the general applicability of results from this study.

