3.3. Sample Size Considerations

This study is descriptive in nature, as such the sample size for this study is determined by practical rather than statistical considerations. Approximately 79 subjects will be enrolled to achieve at least 79 treated subjects with evaluable post-baseline tumor data. With 79 subjects, the precision for point estimate for ORR is as follows: the 95% confidence interval (CI) width for ORR based on Wilson score intervals are at most the observed proportion +/- 0.108. If the observed ORR = 30.4% (24 of 79 subjects with PR or CR), the lower bound of the 95% CI would be 19.5%.

Of the 79 subjects enrolled, an estimated 50 subjects will be enrolled with gastric or GEJ cancer, and an estimated 29 subjects will be enrolled with esophageal cancer. Assuming at least 50 evaluable gastric/GEJ subjects are evaluable for ORR, the precision for point estimate for ORR is as follows: the 95% CI width for ORR based on Wilson score intervals are at most the observed proportion +/- 0.134. Assuming at least 29 evaluable esophageal cancer subjects are evaluable for ORR, the precision for point estimate for ORR is as follows: the 95% CI width for ORR based on Wilson score intervals are at most the observed proportion +/- 0.173.

Sponsor: Aduro Biotech, Inc.
Protocol Number: ADU-CL-14
Version and Date: Version 1.0, 13Mar2018

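### The lower 95% bound given for 24/79 responders is 19.5%, but the Wilson interval the plan names gives 21.3%; the three plus-or-minus limits on ORR precision are also slightly too small as worded

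*Protocol*

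**What the plan says.** Protocol 6.5.1 describes the sample size only through the precision of the ORR estimate. For all 79 subjects it states that the "95% confidence interval (CI) width for ORR based on Wilson score intervals are at most the observed proportion +/- 0.108". It then gives a worked example: "observed ORR = 30.4% (24 of 79 subjects with PR or CR), the lower bound of the 95% CI would be 19.5" percent. The same form of statement follows for the 50 gastric/GEJ subjects ("95% CI width for ORR based on Wilson score intervals are at most the observed proportion +/- 0.134") and for the 29 esophageal subjects ("95% CI width for ORR based on Wilson score intervals are at most the observed proportion +/- 0.173").

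The synopsis repeats the n = 79 limit and the worked example. SAP 3.3 repeats every figure, including "the lower bound of the 95% CI would be 19.5" percent. Protocol 6.5.2 fixes the level ("All CIs will be 95%, unless stated otherwise"), and Protocol 6.5.5.1 names the Wilson score interval for the ORR analysis. The method and level behind these figures are therefore not in doubt.

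**The concern.** A Wilson interval is centred on a value pulled towards 50%. For an observed rate below 50%, the lower limit is closer to that rate than the upper limit is. A lower bound 10.9 points below 30.4% is therefore suspect on sight. It is also slightly farther away than the 0.108 that the preceding sentence allows. The same asymmetry casts doubt on any limit expressed as the observed proportion plus or minus a constant.

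At stake is the accuracy of the plan's only numerical statement of what 79, 50 and 29 subjects deliver for the primary efficacy variable. The statement appears in full in two places and in part in a third.

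**Working it through.** **Inputs.** x = 24 and n = 79, with subgroup sizes 50 and 29 (Protocol 6.5.1); 95% level (Protocol 6.5.2), so z = 1.95996 and z² = 3.8415; Wilson score method (Protocol 6.5.1 and 6.5.5.1).

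**Formula.** With p = x/n:
- centre = (p + z²/2n) / (1 + z²/n)
- half-width = z / (1 + z²/n) × √[p(1 − p)/n + z²/4n²]

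**Step 1: the interval for 24/79.** Here p = 0.3038.
- centre = (0.3038 + 0.0243) / 1.0486 = 0.3129
- half-width = (1.95996 / 1.0486) × √(0.002677 + 0.000154) = 0.0995
- interval = 0.3129 ± 0.0995 = 0.2134 to 0.4123

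The lower limit is 0.0904 below p and the upper limit is 0.1085 above it. The stated 19.5% is 1.8 points below the correct 21.3%.

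**Step 2: where 19.5% comes from.** Other 95% methods give these lower bounds at 24/79: Wald 20.2%, Clopper-Pearson 20.5%, Wilson with continuity correction 20.8%, Jeffreys 21.1%, Agresti-Coull 21.3%. None gives 19.5%. Subtracting the upper distance from p does: 0.30380 − 0.10855 = 0.19525. The upper arm was mirrored below the observed rate.

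**Step 3: where 0.108, 0.134 and 0.173 come from.** They equal the larger distance from p to a Wilson limit at the count nearest 50%: 0.1080 at 39/79, 0.1336 at 25/50 and 0.1729 at 14/29. One convention reproduces all three.

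**Step 4: why these are not maxima.** Each Wilson limit L satisfies |L − p| = z√[L(1 − L)/n]. The distance is largest when the limit itself, not p, is at 50%, and its ceiling is z/(2√n). That ceiling is 0.1103 for n = 79, 0.1386 for n = 50 and 0.1820 for n = 29. By contrast, the half-width about the Wilson centre does peak at p = 50%, at z/(2√(n + z²)).

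| n | Stated | Maximum half-width about the Wilson centre | Largest distance from p (count) | Upper distance at about 30% |
|---|---|---|---|---|
| 79 | 0.108 | 0.1077 | 0.1103 (31/79) | 0.1085 (24/79) |
| 50 | 0.134 | 0.1336 | 0.1386 (18/50) | 0.1375 (15/50) |
| 29 | 0.173 | 0.1710 | 0.1820 (9/29) | 0.1820 (9/29) |

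At most, the stated values fall short by 0.1103 − 0.108 = 0.0023, 0.1386 − 0.134 = 0.0046 and 0.1820 − 0.173 = 0.0090. For rates up to 50% only the upper distance exceeds them; the lower distance never does.

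**Step 5: where the limits hold.** For n = 79, 0.108 holds at 17/79 (0.1027) and 22/79 (0.1073) and fails at the plan's own example, 24/79 (0.1085). For n = 50, 0.134 holds at 11/50 (0.1324) and fails at 14/50 (0.1367). For n = 29, 0.173 already fails at 6/29 (0.177).

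**The case against.** The strongest reply is that little depends on these numbers. Protocol 6.5.1 and 6.1.1 set the size on practical grounds, Protocol 6.5.2 plans no hypothesis test, and SAP 7, 7.1 and 11 confine efficacy to subject listings, so no ORR interval will be reported under the current SAP. The lower-bound error is also cautious, because it makes the evidence look weaker than it would be. All of this stands and limits the weight of the point. It does not make 19.5% correct.

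A second reply is that the plus-or-minus sentences are about interval width. Read as half-widths about the Wilson centre, 0.108 and 0.134 are exact to three decimals, and 0.173 is a valid but loose bound (the maximum is 0.171). This is a fair reading of the intent, but the sentences attach the figures to the observed proportion, where they fail. It also leaves the 19.5% unexplained.

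Three stronger readings are tempting and are not supported:

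- **That the limits fail at the response rates the trial expects.** The documents state no expected ORR. At n = 79 the limit holds at counts matching the 22% and 28% benchmarks in Protocol 6.1.1. The failure can be claimed at about 30%, the plan's worked rate.
- **That the error changes how many responders are needed to exceed 22%.** The plan sets no such requirement. The 22% is one reference figure, and in the worked example both 19.5% and 21.3% lie below it.
- **That the esophageal 29 contradicts Protocol 6.2.** That section says "enrollment will be targeted to a minimum of 26 subjects with esophageal cancer". A floor of 26 and an estimate of 29 can both hold, and 6.5.1 makes its precision statement conditional on at least 29 evaluable subjects.

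**Conclusion.** The 19.5% is wrong as written in all three places. Under the plan's own method and level the lower bound at 24/79 is 21.3%, and the interval is 21.3% to 41.2%. The plus-or-minus limits are too small as worded, by at most about 0.002 (n = 79), 0.005 (n = 50) and 0.009 (n = 29). They slightly overstate precision, whereas the lower-bound error understates it.

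The result assumes only a two-sided 95% Wilson interval without continuity correction; with the correction the lower bound is 20.8%, still not 19.5%. The point is minor. It corrects a stated figure for the primary efficacy variable and does not alter the design, the sample size or any result the SAP will report.

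**What to change.** In the Protocol synopsis, Protocol 6.5.1 and SAP 3.3, replace 19.5% with 21.3% and give the whole interval, 21.3% to 41.2%.

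Restate the precision limits in one of two ways, and say which is meant:
- maximum half-width about the Wilson centre: 0.108 (n = 79), 0.134 (n = 50), 0.171 (n = 29); or
- farther limit at most 0.110, 0.139 and 0.182 from the observed rate, noting that the interval is not centred on that rate.

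The synopsis needs only the n = 79 figure. The cost is a text correction: no change to design, data collection or analysis programs.

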6.5.2 General Considerations

The descriptive summary for the categorical variables will include counts and percentages. The descriptive summary for the continuous variables will include means, medians, standard deviations, Q1, Q3, and minimum and maximum values. The descriptive summaries of time to event data will include median, 25th and 75th percentiles, and standard error. All data will be listed for all subjects.

This study is descriptive in nature; no formal hypothesis testing will be performed. All CIs will be 95%, unless stated otherwise.

All statistical analyses will be performed using SAS.

The effects of noncompliance, dropouts, and covariates will be assessed to determine the impact on the general applicability of results from this study.

6.5.3 Subject Information

Subject disposition summaries will include the number of enrolled subjects, the number of subjects receiving study drug, the number of subjects completing the study, the number of subjects withdrawing prematurely, and the reasons for treatment and study discontinuation.

Demographics and baseline disease characteristics will be summarized using descriptive statistics.

6.5.4 Analysis Sets

Evaluable Analysis Set (EAS) is defined as all subjects who received at least 1 dose of CRS-207 and have at least one evaluable post-baseline RECIST tumor response assessment or were discontinued due to toxicity. The EAS will be the primary population for analyses of tumor-related endpoints (ORR, DCR, DOR, and PFS).

Full Analysis Set (FAS) is defined as all subjects who received at least 1 dose of CRS-207. The FAS will be used for analyses of OS, immunogenicity and other biomarker data, and sensitivity analysis of select tumor-related endpoints.

Safety Set (SAF) includes all subjects who received any study treatment (pembrolizumab or CRS-207). The SAF will be used for all analyses of safety data and may be used for select biomarker data.

Additional analysis sets (e.g. per protocol set) may be defined in the SAP.

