Tumor imaging and evaluation will be assessed at Screening and during the Treatment and Evaluation Period approximately every 6 weeks after initiation of study drug. Tumor measurement and assignment of response will be determined by local Investigators. For subjects on treatment more than 12 months, the frequency of imaging may be reduced to every 12 weeks. Peripheral blood will be collected to assess immune responses directed against *Lm*, mesothelin, and other tumor-associated antigens. Archived tumor tissue and paired tumor biopsies (collected at Screening and during Cycle 2) will be used to explore the association of PD-L1 expression, mesothelin expression, and TIL characteristics with clinical responses.

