6.5.5.1 Primary Efficacy Variable and Analysis

The ORR is defined as the proportion of subjects with best overall response (BOR) of partial response (PR) or complete response (CR) according to RECIST v1.1. The proportion of subjects with ORR in the EAS, along with a 95% CI based on the Wilson Score interval, will be reported. Analyses of ORR described above may be repeated in FAS, treating missing BOR as a non-responder. Objective disease response at each visit and best overall response will also be summarized using the EAS.

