6.5.5.2 Secondary Efficacy Variables and Analyses

Secondary efficacy variables in the study include:

Disease control rate (DCR) defined as the percentage of subjects with BOR of CR, PR, or SD. The analysis of DCR will be performed using the EAS and conducted in the same manner as ORR.

Progression-free survival (PFS) defined as time from first dose of study drug to first documentation of disease progression (per RECIST) or death due to any cause.

Subjects who do not experience disease progression and are alive on or before the data cut-off date will be censored at the time of last evaluable tumor assessment or data cut-off date, whichever is earlier. Subjects who do not experience disease progression and start new systemic anti-cancer therapy will be censored at the last evaluable tumor assessment on or prior to the time the new systemic anti-cancer therapy was begun or the data cut-off date, whichever is earlier. For analyses conducted in the FAS, subjects with no evaluable post-baseline tumor assessments will be censored at the time of receipt of first study drug. Subjects who are lost to follow-up for assessment of disease progression will be censored at their last evaluable tumor assessment or data cut-off date, whichever is earlier. The analysis of PFS will be performed in the EAS using Kaplan-Meier methods. Analyses may be repeated in the FAS.

Duration of response (DOR) includes subjects with an objective disease response (PR or CR) and is defined as the time from the first tumor assessment that supports the subject's objective

disease response to the time of disease progression or death due to any cause. Subjects who do not experience disease progression or death at the time of analysis will be censored using the same rules as described for PFS. The analysis of DOR will be performed in the EAS using Kaplan-Meier methods.

Overall Survival (OS) defined as the time from first dose of study drug until date of death due to any cause. Subjects without documentation of death at the time of analysis will be censored as of the date the subject was last known to be alive, or the data cut-off date, whichever is earlier. OS will be performed in the FAS using Kaplan-Meier methods. The analysis may be repeated in the SAF.

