7.2. Secondary Efficacy Endpoints

Disease Control Rate

Disease control is achieved by subjects who exhibit a BOR of CR, PR, or SD according to RECIST v1.1. DCR is defined as the number of subjects who exhibit a BOR response of CR, PR, or SD divided by the number of subjects evaluable for analysis and will not be summarized or reported in the CSR synopsis.

Progression Free Survival

PFS is defined as the number of weeks from the date of first dose of study treatment to the first date of objectively determined progressive disease according to RECIST v1.1 or death from any cause and is computed as described in Section 5.3. The primary analysis of PFS will include tumor assessments collected after the end of study treatment. Tumor assessments taken after switch to another anti-cancer therapy will be excluded from consideration.

The first date of objectively determined progressive disease would be the earliest date of any post-baseline overall response finding of progressive disease as part of the tumor lesion assessment data or death, unless a subject is censored at an earlier date. If an assessment occurs over several days, the method described in Section 5.6 will be used. If there are no adequate assessments for a subject, they will be censored on their first dose date unless they died prior to having their first assessment (in which case they will be considered to have had a PFS event of death). If a subject receives subsequent anticancer therapy prior to documentation of progressive disease, PFS will be censored at the latest adequate assessment prior to therapy initiation.

Subjects who progress or die following an extended period of follow up will also be censored at a latest adequate assessment prior to the end of a predefined lapse window, even if information is available regarding progression or death after this extended period. Should a subject die after the end of this lapse window they will be censored at their first dose date. The lapse window after which PFS events will not be considered is defined in Section 5.7.

Otherwise, if a subject does not have documented progression, the subject will be censored at the latest adequate assessment.

PFS will be listed.

Sponsor: Aduro Biotech, Inc.
Protocol Number: ADU-CL-14
Version and Date: Version 1.0, 13Mar2018

Overall Survival

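### The protocol's primary set for ORR, DCR and PFS leaves out CRS-207-treated subjects lost before any evaluable scan, and the planned size allows for no such loss

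*Protocol*

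**What the plan says.** Protocol 6.5.4 on the EAS: "The EAS will be the primary population for analyses of tumor-related endpoints (ORR, DCR, DOR, and PFS"). Besides one CRS-207 dose, subjects must "have at least one evaluable post-baseline RECIST tumor response assessment or were discontinued due to toxicity". Imaging is "approximately every 6 weeks after initiation of study drug" (Protocol 6.1), so the first chance to qualify by scan comes at about week 6.

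The FAS needs only one CRS-207 dose. For ORR, Protocol 6.5.5.1 says the analyses "may be repeated in FAS, treating missing BOR as a non-responder". For PFS, Protocol 6.5.5.2 counts death whatever its cause, but in the FAS "subjects with no evaluable post-baseline tumor assessments will be censored at the time of receipt of first study drug", with no stated exception for a subject who died. SAP 7.2 also censors subjects without an adequate assessment at first dose, but "unless they died prior to having their first assessment", in which case the death is an event.

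On size, Protocol 6.5.1: "Approximately 79 subjects will be enrolled to achieve at least 79 treated subjects with evaluable post-baseline tumor data". It splits the 79 enrolled into 50 gastric/GEJ and 29 esophageal, then assumes at least 50 and at least 29 evaluable. No loss rate or replacement rule is given.

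**The concern.** Membership of the primary set depends on something that happens after treatment starts. A responder must have a scan, so nobody removed for lack of one can be a responder, and the ORR denominator shrinks while the numerator stays. The same holds for DCR, because stable disease also needs a scan. For PFS, a death at week 4 without a scan is absent from the EAS and, read literally, carries no information in the FAS.

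Protocol 6.1.1 describes a single-arm study whose response rate is to be read against external benchmarks (7% to 28% in second line; 22% for pembrolizumab in third-line, PD-L1-expressing patients) before a larger randomized trial. With no control arm, nothing cancels an upward shift.

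**Working it through.** **Inputs.** From Protocol 6.5.1: n = 79, 50 and 29; stated maximum half-widths 0.108, 0.134 and 0.173; example 24/79 = 30.4%. Two-sided 95%, z = 1.96. The share d of CRS-207-treated subjects outside the EAS is not in the documents; 5% to 20% is assumed.

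**The plan's own precision.** The Wilson half-width is largest at a proportion of one half, where it equals z / (2√(n + z²)).
- n = 79: 1.96 / (2√82.84) = 0.108, as stated.
- n = 50: 1.96 / (2√53.84) = 0.134, as stated.
- n = 29: 1.96 / (2√32.84) = 0.171, against 0.173 stated.

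The stated lower bound of 19.5% for 24/79 also does not reproduce; Wilson gives 21.3%. That is a separate matter and is not used here.

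**Attrition and ORR.** Evaluable from 79 enrolled is 79(1 − d). Enrolment needed for 79 evaluable is 79/(1 − d), rounded up. ORR over CRS-207-treated subjects is 24 divided by that enrolment, with missing best response as non-response.

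| d (assumed) | Evaluable of 79 | Max half-width | Enrolment for 79 evaluable | 24/79 in EAS becomes |
|---|---|---|---|---|
| 0% | 79 | 0.108 | 79 | 30.4% |
| 5% | 75 | 0.110 | 84 | 24/84 = 28.6% |
| 10% | 71 | 0.113 | 88 | 24/88 = 27.3% |
| 15% | 67 | 0.116 | 93 | 24/93 = 25.8% |
| 20% | 63 | 0.120 | 99 | 24/99 = 24.2% |

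The EAS overstates ORR by the factor 1/(1 − d). Enrolling 79 to obtain at least 79 evaluable works only at d = 0; at d = 5% the chance that all 79 are evaluable is 0.95^79 = 1.7%.

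**PFS.** Take a subject who dies of disease at week 4 with no scan.
- Protocol EAS: not in the set.
- Protocol FAS, read literally: censored at first dose. The subject leaves the risk set before any event and does not affect the Kaplan-Meier curve.
- SAP 7.2: an event at death.

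If q is the share of FAS subjects who die before a scan and are left out, the EAS curve after the first scan time is the true curve divided by (1 − q). Living subjects without a scan do not matter here: censored at day 0, they leave the curve unchanged. As an illustration only, assume exponential PFS with a true median of 3.0 months. The EAS median solves S(t) = 0.5(1 − q), so t = 3.0 × [1 − ln(1 − q)/ln 2], which gives 3.2, 3.5, 3.7 and 4.0 months at q = 5%, 10%, 15% and 20%. The upper values require every lost subject to have died, so q is at most d.

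**The case against.** Several points on the other side stand and limit the claim.

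- A reader might infer that the trial's reported results are inflated. The documents do not support this. SAP 3.5 records that development stopped on 12 December 2017. SAP 6.1 uses only the SAF, SAP 7 and 7.1 list efficacy without summarizing it, and SAP 11 declares that change.
- A reader might infer that everyone who declines before week 6 is dropped. Protocol 6.4.2.1 asks subjects who stop treatment without documented progression to continue 6-weekly imaging, so some remain evaluable, and toxicity discontinuations stay in without a scan. Those removed also include withdrawals and unevaluable scans, not only treatment failures.
- The protocol does not say that deaths are censored. Its general censoring rule is limited to living subjects, and the FAS sentence can be read in that light. What stands is that the sentence has no such limit, and the SAP needed an explicit exception.
- The FAS analysis is not wholly optional: Protocol 6.5.4 assigns the FAS to sensitivity analysis of selected tumor endpoints, and 6.5.2 promises an assessment of dropouts. Neither names ORR or PFS, and the sections that do say only that the analyses may be repeated.
- The FAS is not all treated subjects. CRS-207 follows pembrolizumab by a day in Cycle 1, so subjects given pembrolizumab alone are only in the SAF.
- On size, the protocol says that "the sample size for this study is determined by practical rather than statistical considerations", no test depends on it, and 79 is elsewhere described as an evaluable count. The loss of precision is modest.

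**Conclusion.** The point holds as a protocol design flaw of moderate weight. The upward direction for ORR follows from the EAS definition and needs no assumption, and any early death left out is a lost PFS event. The size is unknown: at an assumed loss of 5% to 20%, 30.4% in the EAS corresponds to 28.6% to 24.2% of CRS-207-treated subjects, and the maximum half-width is 0.110 to 0.120. From 10% loss upward, the protocol's example falls from above to below the 28% top of its second-line range. The documents do not give the benchmarks' own denominators, so that comparison shows scale only.

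The CSR synopsis will carry no biased estimate. What remains affected is any ORR, DCR or PFS computed under the protocol. Estimates computed from the listings are also exposed: SAP 7.1 and 7.2 divide ORR and DCR by a count of evaluable subjects that the SAP never defines, and the two documents' wording on early death differs.

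**What to change.** - Make the FAS (at least one CRS-207 dose) primary for ORR and DCR, with missing best response counted as non-response, as Protocol 6.5.5.1 already allows for ORR.
- Make the FAS primary for PFS, with death before the first scan an event at the date of death. Moving to the FAS without this change would not restore those events. Limit first-dose censoring to living subjects without a scan.
- Take only the early-death clause from SAP 7.2. The same section censors deaths after the lapse window at first dose, so adopting it whole would bring back the same kind of defect.
- Keep the EAS as a supportive set, and define the evaluable denominator in SAP 7.1 and 7.2.
- Restate the size in Protocol 6.5.1 as about 79 CRS-207-treated subjects in the FAS. The 0.108 then applies without enrolling more.

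The cost is wording. Deaths are already collected under Protocol 6.4.2.2. The downside is a somewhat lower reported ORR.
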